### 7.3 Subject Population(s) for Analysis

Any subject with study data at Baseline visit or later will be subjected to study analysis.

## 8 Safety and Adverse Events

### 8.1 Definitions

#### Unanticipated Problems Involving Risk to Subjects or Others

Any incident, experience, or outcome that meets all of the following criteria:

- Unexpected in nature, severity, or frequency (i.e. not described in study-related documents such as the IRB-approved protocol or consent form, the investigators brochure, etc.)

CONFIDENTIAL

This material is the property of the University of Pennsylvania. Do not disclose or use except as authorized in writing by the study sponsor

- Related or possibly related to participation in the research (i.e. possibly related means there is a reasonable possibility that the incident experience, or outcome may have been caused by the procedures involved in the research)
- Suggests that the research places subjects or others at greater risk of harm (including physical, psychological, economic, or social harm).

### **Adverse Event**

An **adverse event** (AE) is any symptom, sign, illness or experience that develops or worsens in severity during the course of the study. Intercurrent illnesses or injuries should be regarded as adverse events. Abnormal results of diagnostic procedures are considered to be adverse events if the abnormality:

- results in study withdrawal
- is associated with a serious adverse event
- is associated with clinical signs or symptoms
- leads to additional treatment or to further diagnostic tests
- is considered by the investigator to be of clinical significance

### **Serious Adverse Event**

Adverse events are classified as serious or non-serious. A **serious adverse event** is any AE that is:

- fatal
- life-threatening
- requires or prolongs hospital stay
- results in persistent or significant disability or incapacity
- a congenital anomaly or birth defect
- an important medical event

Important medical events are those that may not be immediately life threatening, but are clearly of major clinical significance. They may jeopardize the subject, and may require intervention to prevent one of the other serious outcomes noted above. For example, drug overdose or abuse, a seizure that did not result in in-patient hospitalization or intensive treatment of bronchospasm in an emergency department would typically be considered serious.

All adverse events that do not meet any of the criteria for serious should be regarded as **non-serious adverse events**.

### **Adverse Event Reporting Period**

The study period during which adverse events must be reported is normally defined as the period from the initiation of any study procedures to the end of the study treatment follow-up. For this study, the study treatment follow-up is defined as 30 days following the last administration of study treatment.

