### **6.5 Visit 2**

Participants will repeat all measures from Visit 1 at this study visit on their first thyroid preparation (LT4 or LT3). Subjects will stop taking study drug for 4 weeks after the study visit 2. During this wash-out period once every two weeks a phone contact will continue to be made by one of the study team members to inquire if the participant has experienced any adverse events. Specifically, the participant will be asked if they have any symptoms

CONFIDENTIAL

This material is the property of the University of Pennsylvania. Do not disclose or use except as authorized in writing by the study sponsor

of palpitations or shortness of breath. A six week supply of crossover study drug will either be sent home with the participant from study visit 2 or it will be mailed to them. Subjects will be instructed to begin this study drug 4 weeks after study visit 2. TSH level will be checked 4 weeks after starting the new study drug, and all study procedures for medication titration and TSH checks will be repeated as above.

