## **6.6 Visit 3**

Participants will repeat all measures from Visit 2 at this final study visit on their second thyroid preparation (LT4 or LT3). The study will be complete.

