## **6.7 Phone Contacts**

Once during the first week, a phone contact will be made by one of the study team members to inquire if the participant has experienced any adverse events following LT4 or LT3 supplementation. Thereafter, once every two weeks a phone contact will be made by one of the study team members to inquire if the participant has experienced any adverse events following drug supplementation. Specifically, the participant will be asked if they have any symptoms of palpitations or shortness of breath. Additionally, one day following each TRH administration (study Visits 1, 2, and 3) a phone contact will be made by one of the study team members to inquire if the participant has experienced any adverse events following study drug injection. If the participant experiences any adverse events following the final phone contact, they will have an emergency phone number to contact, which is [contact] as noted on the front of the informed consent document and utilized throughout the entire study.

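### Adverse events must be recorded for 30 days after the last study treatment, but no contact is explicitly scheduled beyond the day after Visit 3

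*Combined protocol and SAP*

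**What the plan says.** Section 8.1 (Adverse Event Reporting Period) sets the span in which events must be reported as "the period from the initiation of any study procedures to the end of the study treatment follow-up", and adds that "the study treatment follow-up is defined as 30 days following the last administration of study treatment". Section 8.2 says that all adverse events in the study period are to be recorded, and that the investigator asks about them at each contact.

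The contact schedule is in Section 6:

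- After Visit 2 (6.5), "Subjects will stop taking study drug for 4 weeks after the study visit 2". Contact goes on: "During this wash-out period once every two weeks a phone contact will continue to be made by one of the study team members", to ask about adverse events.
- After every TRH injection (6.7), "one day following each TRH administration (study Visits 1, 2, and 3) a phone contact will be made".
- Visit 3 (6.6) takes place "at this final study visit on their second thyroid preparation (LT4 or LT3). The study will be complete". The monitoring plan in 10.1 likewise treats a participant as having completed at the final visit on the second treatment.
- After that (6.7): "If the participant experiences any adverse events following the final phone contact, they will have an emergency phone number to contact".

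The Post-study Adverse Event paragraph of 8.1 adds an instruction, given at the last scheduled visit, to report later events that the participant or personal physician thinks may reasonably be related to taking part.

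**The concern.** The safety section sets a duty that runs for a month past the point where the procedures section stops. Under 8.2 events are elicited at contacts, so a stretch without contacts yields mainly what participants choose to volunteer. The instruction they are given is also narrower than the duty: it covers events believed related, whereas 8.1 and 8.2 cover all events.

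The interval after the first preparation is handled differently, with planned calls through the wash-out. Events after stopping are thus sought in one period and largely left to the participant in the other. A reader of the safety tables could take a lower count after the second preparation for a real difference.

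The monitoring plan has the same gap. The internal medical monitor reviews each participant after completion, and 10.1 places completion at the final visit. That review can therefore come before the 30 days are over.

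**Working it through.** The plan gives no figure to reproduce here. The check sets the required window against the written contacts.

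**1. Start of the window.** Section 5.4 lists TRH among the study drugs and has it given at each study visit, so the last administration is no earlier than Visit 3. Take Visit 3 as day 0; the window ends on day 30.

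**2. Contacts written down, like for like.**

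| | After Visit 2 | After Visit 3 |
|---|---|---|
| Day-after-TRH call (6.7) | 1 | 1 |
| Two-weekly adverse event calls off drug (6.5, 6.7) | 28 / 14 = 2 | none stated |
| Total | about 3 | 1 |
| Last off-drug call | about day 28 | day 1 |
| Days of 30 after that call | 30 − 28 = 2 | 30 − 1 = 29 (97%) |
| What follows | calls resume on the second drug, so the last 2 days are asked about in retrospect | participant-initiated reporting |

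**3. Do the two-weekly calls stop at Visit 3?** Section 6.7 gives them no end date, so this is an inference. Four things support it: 3.4 ties the two-weekly symptom calls to time on study drug; 6.5 makes a specific extension for the wash-out; 6.6 says "The study will be complete" and 10.1 agrees; and 6.7 itself speaks of a final phone contact.

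**4. Is the window empty of exposure?** Section 1.2 gives half-lives of six to eight days for LT4 and one to two days for LT3. Assuming simple exponential decline, the fraction left 14 days after stopping is:

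- LT4: 0.5^(14/6) = 0.20 to 0.5^(14/8) = 0.30.
- LT3: at most 0.5^(14/2) = 0.008.

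Participants who take LT4 second therefore still carry some drug well after the last written call.

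**5. Participants affected.** With 30 enrolled and the 15% dropout of Section 7.1, 30 × 0.85 = 25.5, so about 25 to 26 completers.

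**The case against.** The strongest reply is that a reporting period is not a contact schedule. Section 8.1 promises no active questioning to day 30, and passive reporting after the last visit is compatible with it. There are also safeguards beyond the emergency number: the instruction at the last visit, follow-up of unresolved events until they resolve or are explained, and, in 8.2, recording of possibly related serious events even after the study period. More contact is to be expected in the wash-out, when the participant is still in the trial. Days without a call are also a crude measure, since each call asks about the time since the one before.

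Much of this stands. It rules out saying that events after Visit 3 are not collected at all, and it makes three calls against one a fairer summary than 29 uncovered days. It does not close the gap. None of the safeguards is a scheduled contact, and the instruction reaches only events believed related.

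Two stronger readings are tempting, and the documents do not support either:

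- **That the LT4–LT3 safety comparison is biased.** Order is randomized (5.3), so the difference is by period and each drug should come second in some participants. Section 7.2 plans no adverse event comparison by drug or period. Unequal sequences could carry the effect over to the drugs, but nothing shows that this would occur or how large it would be.
- **That the 14-week minimum follow-up in 4.4.1 proves the window was left out.** The shortest path is 4 + 4 + 4 = 12 weeks, and adding 30 / 7 = 4.3 gives 16.3, which exceeds 14. But the plan does not say how 14 weeks was derived, and 3.1 uses the same figure for the length of supplementation. No weight is placed on it.

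**Conclusion.** The point holds as a mismatch between sections. Recording of all adverse events is required to day 30, one call is explicitly scheduled on day 1, and for the remaining 29 days collection is participant-initiated and partly limited to events believed related. Against about three calls after Visit 2, off-drug events after the second preparation are likely to be under-collected. How many would be missed cannot be estimated from the documents.

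The conclusion rests on reading the two-weekly calls as ending at Visit 3. If the sponsor means them to continue, the practical gap closes, but the text still has to say so. Questioning while on drug follows the same rules in both periods, and the primary endpoints do not depend on it. This is a low-priority correction to safety ascertainment.

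**What to change.** Reconcile 6.6 and 6.7 with 8.1:

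- Extend the two-weekly calls to about two and four weeks after Visit 3, asking about all adverse events as in the wash-out. Placing the second call on or just after day 30, rather than day 28, lets it look back over the whole window.
- End each participant's adverse event follow-up at that last call, and use the same end point for the per-participant safety review in 10.1.
- Check the follow-up range in 4.4.1 and the consent form for consistency.

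Cost: 2 calls × 25 to 26 completers = 50 to 52 short calls (60 if nobody drops out), made by the existing team, and about four more weeks of follow-up per participant. No visit, test or new staff is needed.

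If calls are not wanted, the minimum is to state in 8.1 that reporting after the day-after call is participant-initiated, and to widen the last-visit instruction to all adverse events within the 30 days. That removes the contradiction but leaves the difference in ascertainment between periods.

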### **Preexisting Condition**

CONFIDENTIAL

This material is the property of the University of Pennsylvania. Do not disclose or use except as authorized in writing by the study sponsor

A preexisting condition is one that is present at the start of the study. A preexisting condition should be recorded as an adverse event if the frequency, intensity, or the character of the condition worsens during the study period.

### **General Physical Examination Findings**

At screening, any clinically significant abnormality should be recorded as a preexisting condition. At the end of the study, any new clinically significant findings/abnormalities that meet the definition of an adverse event must also be recorded and documented as an adverse event.

### **Post-study Adverse Event**

All unresolved adverse events should be followed by the investigator until the events are resolved, the subject is lost to follow-up, or the adverse event is otherwise explained. At the last scheduled visit, the investigator should instruct each subject to report any subsequent event(s) that the subject, or the subject's personal physician, believes might reasonably be related to participation in this study. The investigator should notify the study sponsor of any death or adverse event occurring at any time after a subject has discontinued or terminated study participation that may reasonably be related to this study. The sponsor should also be notified if the investigator should become aware of the development of cancer or of a congenital anomaly in a subsequently conceived offspring of a subject that has participated in this study.

### **Abnormal Laboratory Values**

A clinical laboratory abnormality should be documented as an adverse event if any one of the following conditions is met:

- The laboratory abnormality is not otherwise refuted by a repeat test to confirm the abnormality
- The abnormality suggests a disease and/or organ toxicity
- The abnormality is of a degree that requires active management; e.g. change of dose, discontinuation of the drug, more frequent follow-up assessments, further diagnostic investigation, etc.

### **Hospitalization, Prolonged Hospitalization or Surgery**

Any adverse event that results in hospitalization or prolonged hospitalization should be documented and reported as a serious adverse event unless specifically instructed otherwise in this protocol. Any condition responsible for surgery should be documented as an adverse event if the condition meets the criteria for an adverse event.

Neither the condition, hospitalization, prolonged hospitalization, nor surgery are reported as an adverse event in the following circumstances:

- Hospitalization or prolonged hospitalization for diagnostic or elective surgical procedures for a preexisting condition. Surgery should **not** be reported as an outcome of an adverse event if the purpose of the surgery was elective or diagnostic and the outcome was uneventful.
- Hospitalization or prolonged hospitalization required to allow efficacy measurement for the study.

CONFIDENTIAL

This material is the property of the University of Pennsylvania. Do not disclose or use except as authorized in writing by the study sponsor

- Hospitalization or prolonged hospitalization for therapy of the target disease of the study, unless it is a worsening or increase in frequency of hospital admissions as judged by the clinical investigator.

## **8.2 Recording of Adverse Events**

At each contact with the subject, the investigator must seek information on adverse events by specific questioning and, as appropriate, by examination. Information on all adverse events should be recorded immediately in the source document, and also in the appropriate adverse event module of the case report form (CRF). All clearly related signs, symptoms, and abnormal diagnostic procedures results should be recorded in the source document, though should be grouped under one diagnosis.

All adverse events occurring during the study period must be recorded. The clinical course of each event should be followed until resolution, stabilization, or until it has been determined that the study treatment or participation is not the cause. Serious adverse events that are still ongoing at the end of the study period must be followed up to determine the final outcome. Any serious adverse event that occurs after the study period and is considered to be possibly related to the study treatment or study participation should be recorded and reported immediately.

## **8.3 Reporting of Serious Adverse Events and Unanticipated Problems**

Investigators and the protocol sponsor must conform to the adverse event reporting timelines, formats and requirements of the various entities to which they are responsible, but at a minimum those events that must be reported are those that are:

- related to study participation,
- unexpected, and
- serious or involve risks to subjects or others  
(see definitions, section 8.1).

If the report is supplied as a narrative, the minimum necessary information to be provided at the time of the initial report includes:

• Study identifier

• Study Center

• Subject number

• A description of the event

• Date of onset

	

• Current status

• Whether study treatment was discontinued

• The reason why the event is classified as serious

• Investigator assessment of the association between the event and study treatment

---	--

### **8.3.1 Investigator reporting: notifying the study sponsor**

Any study-related unanticipated problem posing risk of harm to subjects or others, and any type of serious adverse event, must be reported to the study sponsor by telephone within seven days of becoming aware of the event. To report such events, a Serious Adverse Event (SAE) form must be completed by the investigator and emailed or faxed

CONFIDENTIAL

This material is the property of the University of Pennsylvania. Do not disclose or use except as authorized in writing by the study sponsor

to the study sponsor within 10 days of becoming aware of the event. The investigator will keep a copy of this SAE form on file at the study site. Report serious adverse events by phone and email or facsimile to:

[name], PhD, [contact], email: [contact]

Within the following 48 hours, the investigator must provide further information on the serious adverse event or the unanticipated problem in the form of a written narrative. This should include a copy of the completed Serious Adverse Event form, and any other diagnostic information that will assist the understanding of the event. Significant new information on ongoing serious adverse events should be provided promptly to the study sponsor.

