### **Reporting Deaths: more rapid reporting requirements**

Deaths that occur during the course of a research study and that are:

- Unexpected; AND
- Related to the research study; AND
- When other participants are believed to be at an increased risk of harm

Must be reported to the IRB within 3 days from the time the investigator becomes aware of the death.

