#### **8.3.3 Sponsor reporting: Notifying the FDA**

The study sponsor is required to report certain study events in an expedited fashion to the FDA. These written notifications of adverse events are referred to as IND safety

CONFIDENTIAL

This material is the property of the University of Pennsylvania. Do not disclose or use except as authorized in writing by the study sponsor

reports. The following describes the safety reporting requirements by timeline for reporting and associated type of event:

- ***Within 7 calendar days***

Any study event that is:

- associated with the use of the study drug
- unexpected,
- fatal or life-threatening, and

- ***Within 15 calendar days***

Any study event that is:

- associated with the use of the study drug,
- unexpected, and
- serious, but not fatal or life-threatening
  - or–
- a previous adverse event that was not initially deemed reportable but is later found to fit the criteria for reporting (reporting within 15 calendar days from when event was deemed reportable).

Any finding from tests in laboratory animals that:

- suggest a significant risk for human subjects including reports of mutagenicity, teratogenicity, or carcinogenicity.

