## 10 Study Monitoring, Auditing, and Inspecting

### 10.1 Study Monitoring Plan

Internal medical monitoring will be performed by [name], who will oversee the safety and validity of the study, according to the University of Pennsylvania Sponsor-Investigator Standard Operating Procedures. In addition, an external medical monitor who is not a study investigator will perform safety monitoring.

Safety monitoring will include careful real-time assessment and appropriate reporting of AEs and SAEs. Safety assessments will be performed by the internal medical monitor after each subject has completed the study (baseline study visit through final visit on treatment 2), and by the external medical monitor after the first, fifteenth, and thirtieth participants have completed the study. All subjects who experiences and/or discontinued due to AEs will be reviewed for key safety data. A final safety assessment will be performed within 3 months of when the last subject has completed the study.

As the Study Sponsor, the PI assumes responsibility to assure that study activities are being carried out as planned so that deficiencies can be identified and corrected. This study will in addition be monitored by a clinical research professional from the staff of Clinical Research Coordinators working for other investigators at the University of Pennsylvania who will be responsible to complete a monitoring process for this study. The designated monitor is not an active member of this study team. A CV for the monitor will be obtained and updated annually. The CV will be kept on file in the Regulatory Binder. The monitor will receive a current protocol, most recently approved Informed Consent Form, and Case Report Forms prior to each monitoring visit.

All CRFs for the first two subjects completed will be 100% source data verified. In addition, CRF's for the 10th, 20th, and 30th subjects will be 100% source data verified upon study completion. If a greater than 10% error rate is noted during the data review, the monitor will source data verify 100% of the data on a larger sample of active subjects following the monitoring visit. The following variables will be 100% source data verified during the monitoring process:

- Informed Consent
- Inclusion/Exclusion Criteria
- Serious and Non-Serious Adverse Events
- Prohibited concomitant medications.
- Drug accountability (IDS will be responsible for drug accountability. Research staff will return all unused study drugs to IDS.

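### Section 8.3.1 has no faster path for fatal or life-threatening events: the sponsor call may take all 7 days of the FDA limit in 8.3.3, and the SAE form and narrative fall 2 to 5 days after it

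*Combined protocol and SAP*

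**What the plan says.** All of the deadlines are in section 8.3.

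- **Investigator to sponsor (8.3.1).** Any serious adverse event, and any study-related unanticipated problem that poses a risk, "must be reported to the study sponsor by telephone within seven days of becoming aware of the event". The SAE form goes "to the study sponsor within 10 days of becoming aware of the event". The section then says: "Within the following 48 hours, the investigator must provide further information on the serious adverse event or the unanticipated problem". That narrative is to come with a copy of the completed form. No shorter limit is given for fatal or life-threatening events.
- **Sponsor to FDA (8.3.3).** The fastest tier is "Within 7 calendar days", for events that are associated with the study drug, unexpected, and "fatal or life-threatening, and" (nothing follows that last connective, so I read three conditions). Other serious, unexpected, drug-associated events are due "Within 15 calendar days". The section does not say when either clock starts.
- **Investigator to IRB (8.3.2, the paragraph on deaths).** Deaths that are unexpected and related, and where other participants are believed to be at increased risk, carry this rule: "Must be reported to the IRB within 3 days from the time the investigator becomes aware of the death".
- **Who the sponsor is (10.1).** "As the Study Sponsor, the PI assumes responsibility to assure that study activities are being carried out as planned".
- **Who is likely to hear first (6.7).** Study team members make the routine telephone contacts that ask about adverse events.
- **A comparison inside the protocol (8.4).** Any breaking of the blind is reported to the PI, the CTRC and the IRB within 24 hours, and to the FDA within seven calendar days.

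**The concern.** The step from investigator to sponsor feeds the step from sponsor to FDA, so its limit should leave the sponsor time to assess the event and write the report. In 8.3.1 the limit for the call equals the shortest FDA limit, and the limits for the two written documents lie beyond it. Section 8.4 is built the other way round: a fast internal step comes before a 7-day FDA step. As written, a fatal event may be passed on internally more slowly than an unblinding.

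At stake is whether staff who keep to 8.3.1 exactly leave the sponsor able to meet 8.3.3. If the PI is not the first to know, the same delay also holds back information that bears on the stopping criteria in 8.5, while other participants, all aged 70 or older, remain on study drug.

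**Working it through.** The plan states no derived figure to reproduce. The check is a day count.

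**Inputs.** Day 0 is the investigator's awareness of the event. Call: day 7 (8.3.1). Form: day 10 (8.3.1). Narrative: a further 48 hours, or 2 days (8.3.1). FDA limits: 7 and 15 calendar days (8.3.3). IRB limit for the defined deaths: day 3 (8.3.2).

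**Anchor of the 48 hours.** The text gives none, so there are two readings:
- from the call: 7 + 2 = day 9
- from the form: 10 + 2 = day 12

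**Time left = external limit − latest internal day**, with the FDA clock also taken to start on day 0:

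| Step | Latest day | 7-day FDA limit | 15-day FDA limit |
|---|---|---|---|
| Call | 7 | 7 − 7 = 0 | 15 − 7 = 8 |
| Narrative, from the call | 9 | 7 − 9 = −2 | 15 − 9 = 6 |
| Form | 10 | 7 − 10 = −3 | 15 − 10 = 5 |
| Narrative, from the form | 12 | 7 − 12 = −5 | 15 − 12 = 3 |

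The call coincides with the 7-day limit. Only the form and the narrative pass it. Every step falls inside the 15-day limit.

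**Internal consistency of 8.3.1.** If the 48 hours run from the call, the narrative is due by day 9 and must include a form that is not due until day 10, which is 10 − 9 = 1 day later. On that reading the 10-day limit can never bind.

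**Sensitivity to the start of the FDA clock.** The protocol is silent, so there are two cases:
- Clock starts on day 0: the FDA report is due on day 7, and the table applies.
- Clock starts only when the sponsor is told, at the latest on day 7: the report is due by 7 + 7 = day 14. The form then leaves 14 − 10 = 4 days and the narrative 14 − 12 = 2 to 14 − 9 = 5 days. Nothing is late under 8.3.3, but the FDA may hear two weeks after the site did.

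Where the PI is the first to know, the sponsor knows on day 0 and only the first case makes sense.

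**Against the IRB limit for deaths.** The sponsor's call may come up to 7 − 3 = 4 days after the IRB report is due. This is a difference in timing between two recipients. The investigator sends the IRB report directly.

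**The case against.** The strongest reply is that the PI is the sponsor. When the PI knows, the sponsor knows, and the call and form in 8.3.1 become internal paperwork that holds nothing up. The first stopping criterion in 8.5 also turns on what the PI discovers, so it is not delayed in that case. This stands, and it confines the problem mainly to events that another team member learns of first. In a trial where team members make the safety calls, that is an ordinary route. Section 8.3.1 also directs reports to a designated contact; the name is removed from the text reviewed, so I cannot tell whether that person is the PI.

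A second reply is that the FDA report does not wait for the internal documents. Section 8.3.3 accepts the FDA form or a narrative with the minimum content listed at the start of 8.3, and does not ask for the 8.3.1 form first. Section 8.3 also binds everyone to each body's timelines, and 10.1 promises real-time safety assessment. All of this shows that compliance is possible, since the 8.3.1 limits are maxima. It does not shorten them, and 8.3.1 sets no content for the call, so no written information is secured by day 7.

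A reader might infer more than the documents support:
- *That the telephone deadline runs past the FDA limit.* It equals it.
- *That the IRB report of deaths conflicts with 8.3.1.* It goes straight from the investigator, covers only deaths meeting all three conditions, and is not blocked.
- *That FDA reports will be 3 to 5 days late.* Those days describe internal documents, and the narrative's lateness depends on the unstated anchor.
- *That all serious events are affected.* Those in the 15-day tier are not.

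**Conclusion.** The concern holds in a limited form. For drug-associated, unexpected, fatal or life-threatening events, 8.3.1 allows an internal sequence that leaves no time after the call and delivers the written record 2 to 5 days after the FDA limit.

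This rests on two assumptions: that the full stated times are used, and that the FDA clock runs from the site's first awareness. The documents do not state the second. If the clock ran from notice to the sponsor, there would be no formal breach, only a later FDA report. The practical exposure is mainly the case where someone other than the PI hears first. It is a safety-reporting inconsistency worth correcting, in a rare class of events.

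**What to change.** Reconcile 8.3.1, 8.3.3 and 10.1:

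1. Shorten the call and form deadlines in 8.3.1, at least for fatal or life-threatening events, so that both fall well before the 7-day FDA limit. For the call, 24 hours is one option; 8.4 already uses it for reporting a broken blind internally, although for a different event and different recipients.
2. State in 8.3.3 when the FDA clock starts, given that the PI is the sponsor, and whether awareness by another team member starts it.
3. Anchor the 48 hours for the narrative to a named event, so that it is not due before the form it must include.

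The cost is a wording amendment and faster paperwork for rare events in a 30-participant, single-centre study. The endpoints, sample size and statistical analysis do not change.
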